### Diabetes Management Protocol

We will recruit and randomize males and females with a known history of T2D treated with oral antidiabetic agents, short- and long-acting GLP1-RA or insulin therapy. Glycemic target during admission is to maintain BG between 80-180 during the day, while avoiding hypoglycemia < 70 mg/dl.

**Patients treated with oral antidiabetic agents.** Dose of antidiabetic agents will be continued after randomization unless there is contraindication (i.e., eGFR < 30 ml/ml for patients on metformin and SGLT2; pioglitazone and heart failure, history of pancreatitis for DPP4-I or GLP1-RA), or sulfonylurea (eGFR < 30 ml/min or history of severe hypoglycemia). patients will receive

supplemental/correction insulin for BG >200 mg/dL per sliding-scale. The attending physician could adjust oral medications at his/her discretion in the presence of severe glycemic excursions.

**Recommended Insulin starting dose for insulin naïve patients.** If primary care opts to start insulin therapy, the recommended dose of basal insulin is 0.1 unit/kg, given at the same time every day. Dose of oral agents may be continued, but sulfonylurea agents should be reduced by half or stopped to prevent hypoglycemia.

**Patients T2D Treated with Insulin.** Subjects treated with insulin will continue to receive their total daily dose (TDD) and insulin formulation after randomization. Glycemic target during admission is to maintain BG between 80-180 during the day, while avoiding hypoglycemia < 70 mg/dL.

The attending physician could adjust total daily insulin dose following the suggested insulin adjustment protocol:

**Basal Insulin adjustment.**

- Daily basal (glargine, detemir or degludec) insulin dose will be adjusted as follow:
- If the fasting and pre-dinner BG is between 100 - 180 mg/dL in the absence of hypoglycemia the previous day: no change
- If the fasting and pre-dinner BG is between 181 - 250 mg/dL in the absence of hypoglycemia: increase basal insulin by 10% every day
- If the fasting and pre-dinner BG is between 251 - 350 mg/dL in the absence of hypoglycemia: increase basal insulin by 20% every day
- If the fasting and pre-dinner BG is > 350 mg/dL in the absence of hypoglycemia the previous day: increase basal insulin (glargine) dose by 30% every day
- If the fasting and pre-dinner BG is between 70 - 99 mg/dL in the absence of hypoglycemia: decrease TDD (basal and prandial) insulin dose by 10% every day
- If BG <70 mg/dL, the insulin TDD (basal and prandial) should be decreased by 30%.
- If BG <40 mg/dL, the insulin TDD (basal and prandial) should be decreased by 40-50%.

**Supplemental insulin.** Rapid-acting insulin will be administered following the “supplemental/correction insulin scale” protocol followed by the facility.

- If a patient is able and expected to eat most of his/her meals, supplemental insulin will be administered before meals and at bedtime following the “usual” dose of the insulin scale protocol.
- If a patient is not able to eat, supplemental insulin will be administered every 6 hours following the “sensitive” dose of the supplemental insulin scale protocol.\
- Table indicates number of units to be added to scheduled insulin dose.

**BEFORE MEAL**, Supplemental Sliding Scale Insulin (number of units) - Add to scheduled insulin dose.

BG (mg/dL)

< 200	Do not give extra insulin
201-300	Give extra 2 units regular insulin
301-400	Give extra 4 units regular insulin
401-450	Give extra 6 units regular insulin
> 450	Call NP, PA, or MD

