## 6. Procedures Involved

Residents with T2D in subacute and long-term skilled nursing care facilities treated with insulin and/or insulin-secretagogues will be randomized to a standard of care group with POC testing or to real time Dexcom CGM with GTS for up to 60 days of admission.

Patients in the standard of care group will wear a blinded CGM and receive POC testing before meals and bedtime, with providers adjusting oral agents or insulin dose based on POC results. Patients in the intervention CGM group will have a single daily fasting POC testing and will wear a real-time Dexcom G6 with GTS, and providers will adjust oral or insulin therapy based on CGM-GTS profile information.

Nursing staff and primary care will receive education on the CGM technology by our research team.

Education efforts will include general information on the technology, how and when to remove or replace CGM sensors and transmitters, and the hypoglycemia prevention protocol. Treatment of hypoglycemia (POC <70 mg/dl) will be similar in both groups following a standard hospital protocol.

[figure not shown]
CGM alarm settings, and prevention of hypoglycemia protocol. Hypoglycemia alarm will be set to < 85 mg/dl (for prevention for low blood glucose levels). Nursing staff will be instructed to provide 15 grams of carbohydrates in response to a hypoglycemia alarm. For control group (blinded CGM) CGM alarms are turned off, however if the POC is found to be between <80 mg/dl by POC, 15 grams of carbohydrates will be given as a preventive measurement for hypoglycemia (standard of care).

The hyperglycemia alarm will be set at 300 mg/dl. If this occurs, the nursing staff will assess clinical status and perform a POC glucose testing to confirm glucose values. If BG > 300 mg/dl, nursing staff will communicate the high glucose value to the primary care team.

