### Protection against Risks

We will follow safeguards to minimize the risk to our subjects: a) we will carefully monitor capillary BG at the bedside using a hand-held glucose meter, b) only experienced nurses/or phlebotomist will draw blood samples. To prevent significant clinical events, no patients with history of significant liver, renal impairment or cardiac failure will be recruited in this study.

We expect that approximately 20-30% in insulin and sulfonylurea treated patients will experience one or more episodes of hypoglycemia. To minimize the risk of hypoglycemia, the starting dose will be adjusted following a protocol that has been shown effective on insulin adjustment. To avoid hypoglycemia, the total daily dose of insulin will be decreased by 10% for BG between 70-99 mg/dl and by 20% after each episode of hypoglycemia (BG < 70 mg/dl).

**CGM – alarms and hypoglycemia protocol.** We will use a Dexcom CGM device with a modified transmitter able to store and transmit glucose data to different devices including a notebook/IPAD or computer desk located at the nursing station. The use of hypoglycemia alarm set at 85 mg/dl will alert nursing staff and providers that a patient maybe at risk of hypoglycemia. If this occurs, the nursing staff will meet patient in the room to assess clinical status and signs/symptoms of hypoglycemia and will perform a POC glucose testing to confirm glucose values. In addition, a carbohydrate load of 15 grams will be provided to patients as per hospital protocol to avoid hypoglycemia.

**Hyperglycemia alarm** will be set at 300 mg/dl to alert the nursing staff and providers of the risk of clinically significant hyperglycemic complication. If this occurs, the nursing staff will meet patient in the room to assess clinical status and will perform a POC glucose testing to confirm glucose values. If BG > 300 mg/dl, nursing staff will communicate this high glucose value to the primary care team. The primary care team will review patient record and insulin administration prior to determining need for additional corrective rapid-acting insulin. If patient has received corrective insulin within the past 2 hours, additional correction will not be given, and the blood

sugar will be re-checked in 1 hour. If the glucose value continues to rise with a rise indicated by CGM trend arrow, then additional corrective insulin will be given at that time.

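### For a glucose below 70 mg/dL, section 6 cuts the total daily insulin dose by 30% (40-50% below 40 mg/dL), but the section 15 safeguard says 20%; at lower priority, the cardiac failure exclusion stated in section 15 is not in the section 10 list

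*Combined protocol and SAP*

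**What the plan says.** **Section 6, Basal Insulin adjustment.** For a fasting and pre-dinner glucose of 70-99 mg/dL without hypoglycemia, the instruction is to "decrease TDD (basal and prandial) insulin dose by 10% every day". The next two steps are "If BG <70 mg/dL, the insulin TDD (basal and prandial) should be decreased by 30"% and "If BG <40 mg/dL, the insulin TDD (basal and prandial) should be decreased by 40-50"%. The list is introduced as an adjustment of daily basal insulin and names glargine, detemir and degludec.

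**Section 6, Diabetes Management Protocol.** The text leading into that list says the attending physician "could adjust total daily insulin dose following the suggested insulin adjustment protocol".

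**Section 15, Protection against Risks.** This subsection opens with "We will follow safeguards to minimize the risk to our subjects". Its second paragraph says: "To avoid hypoglycemia, the total daily dose of insulin will be decreased by 10"%. In full, the dose "will be decreased by 10% for BG between 70-99 mg/dl and by 20% after each episode of hypoglycemia (BG < 70 mg/dl"). There is no separate step below 40 mg/dL, although section 15 itself defines severe hypoglycemia as a glucose below 40 mg/dL.

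**Eligibility.** The same subsection of section 15 says that patients with a history of significant liver or renal impairment, or cardiac failure, will not be recruited. The exclusion criteria in section 10 are expected MRI, clinically relevant hepatic disease, corticosteroid therapy, end-stage renal disease on dialysis, anasarca, and pregnancy or breast-feeding; patients under 18 are also not recruited. Cardiac failure is not listed. Section 22 says that staff screen on the listed criteria.

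**The concern.** The trigger (glucose below 70 mg/dL) and the quantity reduced (total daily insulin dose) are the same in both places, but the reductions differ. An ethics board reading the risk section and a clinician reading the treatment section would take away different rules for the event the trial aims to reduce.

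The rule is expected to be reached in practice. Section 15 expects about 20-30% of insulin- and sulfonylurea-treated patients to have at least one episode, and quotes 12-35% for insulin regimens. Section 18 plans on 60% and 35% having at least one value below 70 mg/dL. The documents do not settle on one rate and do not give the share of residents on insulin, so the number affected cannot be stated.

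On eligibility, a safeguard promised in the risk section would not be delivered by screening on section 10 as written.

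**Working it through.** The plan states no figure to reproduce. The check compares the passages and applies simple arithmetic to their percentages.

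**1. Do the two sections describe the same rule?**

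| Glucose (mg/dL) | Section 6, cut in TDD | Section 15, cut in TDD |
|---|---|---|
| 70-99 | 10% | 10% |
| 40-69 | 30% | 20% after each episode |
| below 40 | 40-50% | 20% after each episode (no separate step; a value below 40 is also below 70) |

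The 70-99 step agrees, and section 15 says that dosing follows an insulin adjustment protocol. The only such protocol in the document is the one in section 6. The two therefore appear to be one scheme that diverges below 70 mg/dL. No other section reconciles them.

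**2. Dose remaining after one episode.** Fraction remaining = 1 - reduction.

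- 40-69 mg/dL: section 6 leaves 1 - 0.30 = 0.70; section 15 leaves 1 - 0.20 = 0.80. The ratio is 0.80/0.70 = 1.143, so the section 15 dose is 14% higher. The difference is 0.80 - 0.70 = 0.10, or 10 percentage points of the pre-episode TDD.
- Below 40 mg/dL: section 6 leaves 1 - 0.50 = 0.50 to 1 - 0.40 = 0.60; section 15, read literally, leaves 0.80. The difference is 0.80 - 0.60 = 0.20 to 0.80 - 0.50 = 0.30, or 20-30 percentage points.

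None of these depends on the starting dose. No figure is given for repeat episodes: section 15 applies its cut after each one, while section 6 does not say whether its 30% repeats.

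**3. Who is covered?** Residents whose only treatment is an insulin secretagogue have no insulin dose to reduce. Among insulin users, the section 6 list names three basal insulins, but the inclusion criteria also admit residents on NPH, premixed insulin or sliding-scale regular insulin. Whether the steps below 70 mg/dL reach them is unclear, and a resident on sliding scale alone has no scheduled dose to cut. The conflict is clear for residents on scheduled basal insulin and uncertain beyond them.

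**4. Optional or required?** The lead-in in section 6 uses *could* and *suggested*. The list itself then uses *will* for the daily basal adjustment and *should* for the steps below 70 mg/dL. Section 15 uses *will*. Section 6 is thus mixed within itself.

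**5. Cardiac failure.** Section 15 rules it out, section 10 does not list it, and section 22 screens on the list. Anasarca is not an equivalent criterion.

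**The case against.** The strongest reply is that insulin adjustment is left to the attending physician, so neither printed figure fully controls dosing. That limits the practical effect. It does not remove the conflict, because section 15 presents its figure as a participant protection that will be applied.

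A reader might also infer more than the documents support:

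- **A biased primary outcome.** Hypoglycemia is in the primary outcome, and monitoring differs by arm: "Patients in the standard of care group will wear a blinded CGM and receive POC testing before meals and bedtime", while the intervention arm has one fasting POC test plus real-time CGM. The dose rule is nevertheless worded the same for both arms, and nothing in the documents shows a direction or size of effect on any endpoint.
- **A clean split between an optional section 6 and a mandatory section 15.** Section 6 is itself mixed. The opening sentence on safeguards in section 15 introduces only glucose monitoring and who draws blood; the dose sentence comes in the next paragraph, though under the same heading.
- **A conflict that covers every insulin-treated resident.** The basal-insulin heading and the named insulins do not support that.
- **Proof that residents with heart failure are meant to be enrolled.** Section 6 names heart failure as a reason not to continue pioglitazone after randomization. This fits with enrolling them, but the condition could also arise during a stay of up to 60 days.
- **A renal contradiction.** Section 15 does not define *significant* renal impairment, and the phrase may be shorthand for the dialysis criterion in section 10. The same word may qualify cardiac failure, which would leave its threshold open, but section 10 has no cardiac failure criterion of any degree.

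Cardiac failure is a separate matter from the dose rule and is kept here as a minor note.

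**Conclusion.** The dose rule below 70 mg/dL is wrong as written, because sections 6 and 15 cannot both hold. The gap is 10 percentage points of pre-episode TDD at 40-69 mg/dL and, on a literal reading of section 15, 20-30 points below 40 mg/dL. These sizes assume a single episode, a resident on scheduled insulin to whom the section 6 list applies, and that the two sections describe one scheme, as the matching 70-99 step suggests.

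This is a patient-safety inconsistency that should be corrected. The cardiac failure mismatch is also real but of lower priority, and the number of residents it touches is not given. No view is taken on which reduction or which eligibility rule is right.

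**What to change.** 1. Reconcile section 6 (Basal Insulin adjustment) with section 15 (Protection against Risks) so that one rule applies below 70 mg/dL. It should state how a value below 40 mg/dL is handled, which insulin users are covered, and whether the rule is suggested or required. Stating it once, with a cross-reference from the other section, would be enough.
2. Reconcile the recruitment statement in section 15 with the exclusion list in section 10 on cardiac failure.

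The clinical content of both is for the investigators to decide. The cost is a short protocol amendment, with no change to the analysis or the sample size.

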## 7. Data and Specimen Banking

Not applicable

## 8. Sharing of Results with Participants

The result of instant blood sugar will be shared with patients, nurses and health care providers immediately at LTC. However, the final results of the study and its finding will not be shared with participants.

## 9. Study Timelines

The duration of an individual participant's participation in the study will be equal the length of admission to subacute and long-term skilled nursing care facilities (LTC) or up to sixty (60) days, whichever comes sooner.

## 10. Inclusion and Exclusion Criteria

Coordinators will screen for potential participants from the electronic medical record. Subjects will be provided with sufficient information on the practice of glucose monitoring before providing written consent. The process of obtaining informed consent will follow the standard procedures of Emory University. This protocol will be submitted for approval by the Emory IRB.

### Inclusion Criteria:

1. Males and females admitted to subacute and long-term skilled nursing care facilities
2. Known history of T2D treated with insulin (glargine, detemir, degludec, NPH, premixed insulin) or sliding scale regular insulin) or insulin secretagogues (sulfonylureas, repaglinide, nateglinide) with or without additional oral antidiabetic agents (alpha-glucosidase inhibitors, thiazolidinedione, SGLT2- inhibitors, DPP4-inhibitors), short- and long-acting GLP1-RA (exenatide, liraglutide, dulaglutide, semaglutide)
3. Patients with an expected LTC length-of-stay > 1 week

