#### PRELIMINARY RESULTS:

[figure not shown]
**Diabetes and Clinical Outcome in LTC Residents** . In a retrospective study, we analyzed the quality of diabetes care, glycemic control, and clinical outcome in 1,409 subjects admitted to 3 community LTC facilities in Atlanta. The prevalence of diabetes was 34.2%. On admission, patients with diabetes were sliding scale regular insulin (25%), OADs (5%), insulin (34%), or with combination of OADs and insulin (26%). Patients with diabetes had higher number of complications and required more emergency room and hospital transfers. A total of 42% of patients had  $\geq 1$  episode of BG  $<70$  mg/dl and 7% had a BG  $<40$  mg/dl. Hypoglycemia was reported in 45% on OADs (mostly sulfonylurea plus SSI), or insulin therapy. Patients with hypoglycemia had a longer length of stay, higher emergency room or hospital transfers (44% vs. 30%;  $p=0.004$ ) and higher mortality (18% vs. 10%,  $p=0.015$ ). These results indicate that diabetes is common in LTC and is associated with higher resource utilization and complications, and that hypoglycemia is associated with increased rates of emergency room care and hospitalization, length of stay, and mortality.

**Comparing of Oral Antidiabetic Agents and Basal Insulin in LTC Residents with T2D** . In a prospective study we recruited 150 patients from 2 university-affiliated facilities with BG  $> 180$  mg/dl or A1C  $>7.5\%$ , treated with diet and/or with stable dose of OADs or glargin (starting at 0.1 U/kg/day), were randomized to continue OAD plus sliding scale insulin or to basal insulin glargin starting at 0.1 U/kg/day plus SSI for up to 6 months (Fig 1). There were no differences in daily glucose or with the A1C at 3 months or at 6 months or in the number of patients with hypoglycemia (basal 28% vs. control 31%,  $p=0.37$ ). The results of this study indicated similar improvement in glycemic control, without differences in mean daily BG, hypoglycemia with basal insulin or with OADs and SSI supplements. It was also evident that 1/3 od treated with OADs and insulin experienced hypoglycemia indicating the need for safer regimens.

Fig 1-Oral agents vs. Basal Insulin in LTC

B Hypoglycemia

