**DPP4-inhibitors vs Basal insulin in LTC (Linagliptin-LTC Trial).** A 6-month open-label pilot randomized controlled trial compared the efficacy and safety of a DPP4-i (linagliptin) and basal insulin in subacute and LTC residents with T2D admitted to 3 institutions affiliated with Emory University. A total of 140 residents with T2D treated with oral antidiabetic agents or low-dose insulin (0.1 U/kg/d), with fasting BG>180 mg/dL and/or HbA1c >7.5% were randomized to linagliptin 5 mg day or glargin at a starting dose of 0.1 U/kg/d. Baseline antidiabetic therapy, except metformin, was discontinued on trial entry. BG was measured before meals and both groups received supplemental rapid-acting insulin before meals for BG > 200 mg/dL. As shown in Figure 4, treatment with linagliptin resulted in no significant differences in mean daily BG, but resulted in fewer mild hypoglycemic events <70 mg/dL (3% vs. 37%, P <0.001), and a non-significant trend towards lower risk of BG <54 mg/dL (0% vs 7%, p=0.06). There were no significant between-group differences in length of stay, complications, emergency department visits, or hospitalizations. These results suggested that DPP4-inhibitors are effective and represent an alternative to insulin therapy in many LTC residents with T2D.

**Continuous glucose monitoring (CGM) in the hospital setting.** Our research team have reported on 3 RCTs comparing the accuracy of using of CGM and capillary point of care (POC) glucose testing in insulin treated patients with T2D. Increased detection of both hypo- and hyper-glycemic events with the use of CGM compared to POC testing was found. More than 50% of the hypoglycemic occurred at night; suggesting that many of these episodes would be missed by standard POC testing. In a recent study, we compared the performance of the FreeStyle Libre Pro CGM and POC glucose testing among insulin-treated hospitalized patients with T2D. The mean daily glucose was higher by POC testing, and proportions of patients with BG <70 mg/dl and <54 mg/dl by POC BG were lower compared to CGM, all p<0.001 (Fig 3). The overall mean absolute relative difference (MARD), the statistical measure of accuracy used as the standard in glucose monitoring to represent performance, was 14.8%, ranging between 11.4 to 16.7% for glucoses between 70 and 250 mg/dl and the Error Grid analysis showed 98.0% of glucose pairs within Zones A and B.

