The present aims of this RCT is to investigate whether the Dexcom G6 CGM with Glucose Telemetry System (CGM-GTS) with hypoglycemia alarm may reduce the risk of hypoglycemia < 70 mg/dl (safety outcome) and improve glycemic control as measured by the percent of time in range (TIR) 70-180 mg/dl (efficacy end-point) in patients with T2D in subacute and long-term skilled nursing care facilities. Patients in the standard of care group will wear a blinded CGM and receive POC testing before meals and bedtime, with providers adjusting oral agents or insulin dose based on POC results. Patients in the intervention CGM group will have a single daily fasting POC testing and will wear a real-time Dexcom G6 with GTS, and providers will adjust oral or insulin therapy based on CGM-GTS profile information. [name], PhD at the School of Public Health at Emory University will conduct statistical analyses.

For the safety endpoint, we will first compare the proportions of patients who have at least one episode of hypoglycemia by POC and by CGM. We will first perform nonparametric comparisons of the rate of hypoglycemia based on a two-sided Chi-square test (or Fisher's exact test in the presence of low incidence rates), followed by the Cochran-Mantel-Haenszel test, which adjusts for the potential center effect. Then we will perform univariate Poisson regression (or Negative Binomial regression) to assess whether there is any difference in the number of clinically significant hypoglycemia events between the two treatment groups. We will further conduct multivariate Logistic regression, Poisson regression (or Negative Binomial regression) to estimate the difference in the rate and frequency of hypoglycemia while adjusting for potential confounders. A glucose value < 70 mg/dl is considered as hypoglycemia requiring a nurse-driven response; thus, a BG <70 mg/dl will be used for sample size calculation. Data from Singh et al a reduction of hypoglycemia was reported comparing the CGM/GTS system than POC (Singh et al 2020) per patient (0.67 episodes per patient, 95% CI 0.34-1.30

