versus 1.69 episodes per patient, 95% CI 1.11-2.58,  $p= 0.024$ ) . Based on the results of the recent glargine U100 vs U300 study using CGM monitoring in the hospital, 56% had CGM BG readings <70 mg/dl (vs 14% with POC testing-standard of care), it is reasonable to assume 60% of resident on LTC facilities will experience one or more BG < 70 mg/dl by CGM. If we assume that 35% in the standard of care group will have at least one BG <70 mg/dl (based on linagliptin LTC study) , using one-sided, two-sample t-tests, we require we will need 70 patients per group to achieve 80% power.

Hypoglycemia incidence, Rate in the CGM intervention group	30%	35%	40%	45%	50%
Estimated sample size (N/group) for 80% power	49	70	107	186	407

For the efficacy endpoint, we will compare mean daily glucose levels measured by CGM or POC, and percent TIR measured by CGM between treatment groups by nonparametric Wilcoxon-tests or two-sample t-tests, and by multivariate linear regression, which adjusts for other potential confounders such as age, gender, BMI, center, and admission HbA1c. A logarithm transformation may be employed to make the data better conform to the normality assumption. When conducting multivariate regression analyses, we will apply standard variable selection and model checking procedures to decide the final model. Stepwise, backward, or forward model selection strategy will be adopted to determine the variables to be included in the final model. Standard diagnostic and model checking procedures, such as deviance residual plot and Hosmer- Lemeshow test, will be applied to examine the fit of the developed models. To show non-inferiority between POC and CGM in terms of glycemic control, we set the equivalence margin of 18 mg/dl (1 mosm/l), from a view that a difference <18 mg/dl is usually not considered as clinically significant . Based on the results from our recent CGM trials , it is reasonable to assume the standard deviation of mean daily BG is bounded above by 45 mg/dl. Assuming the true BG difference between the treatment groups is zero, and using one-sided, two-sample t-tests, we require 70 subjects for each treatment group to achieve 80% power.

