## 19. Provisions to Monitor the Data to Ensure the Safety of Participants

Baseline and daily information will be entered by the study coordinators into data collection paper forms and into an electronic database (REDCap) provided by the Emory Research Information Technology Department. Baseline data will include demographics/history form (subject gender, age, ethnicity, type of treatment and comorbid conditions, body weight, BMI, laboratory results). Daily information will be collected on treatment, nutrition, blood glucose and laboratory values, complications and adverse events (hypoglycemia). The safety of interventions and treatments associated with this protocol will be under continuous review by

the investigative team. All adverse events will be reviewed bi-weekly in a multidisciplinary format that will involve review by a physician, and other members of the research team. All Serious Adverse Events will be reviewed within the applicable guidelines and submitted to the IRB and other appropriate regulatory bodies governing this study.

In addition, we have implemented protection against risks approaches as above to minimize the risk to our subjects.

**Stopping Rules:** We plan to perform interim analysis on the primary endpoint every 6 months and/or when half of the subjects have been randomized. The trial will be stopped if there is evidence beyond a reasonable doubt of a difference in the rate of death and hospital complications (two-sided alpha level, <0.01) between the treatment groups.

Plans for transmission of temporary or permanent suspension actions:

Any actions that mandate temporary or permanent suspension of study will be transmitted to the Emory IRB, and, if appropriate, to the FDA.

The frequency of protocol review will be: every 6 months.

The PI will forward reports of safety reviews within 15 days of the meeting to the Emory IRB.

See full Data safety monitoring plan in the attachment labeled Data Safety Monitoring Plan  
A Data Safety Monitoring Board or Safety Officer has been designated for this study.

[name]  
Department of Medicine/Endocrinology

[name], MPH  
Department of Medicine/Endocrinology

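### Baseline diabetes regimen defines eligibility but is neither a stated randomization factor nor a prespecified adjuster for hypoglycemia; the likely cost is some precision, not bias

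*Combined protocol and SAP*

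**What the plan says.** Section 10, inclusion criterion 2, lists scheduled insulins and then continues "or sliding scale regular insulin) or insulin secretagogues (sulfonylureas, repaglinide, nateglinide) with or without additional oral antidiabetic agents". A resident can therefore qualify on scheduled insulin, on sliding scale only, or on a secretagogue.

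Section 6 says that residents will be randomized. It gives no method, ratio, blocking or stratification factor.

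Section 18 (data management and statistical analysis) sets out the safety analysis: a two-sided chi-square or Fisher test, then the "Cochran-Mantel-Haenszel test, which adjusts for the potential center effect", then logistic and Poisson or negative binomial models adjusted for potential confounders that are not listed. The efficacy paragraph names "potential confounders such as age, gender, BMI, center, and admission HbA1c" as an open list of examples, and lets stepwise, backward or forward selection decide which variables stay.

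Section 19 shows that baseline data will include "type of treatment and comorbid conditions, body weight, BMI, laboratory results", so the regimen variable will exist.

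The preliminary results in section 3 give some idea of risk by regimen:
- In the linagliptin trial, linagliptin against glargine "resulted in fewer mild hypoglycemic events <70 mg/dL (3% vs. 37%, P <0.001"). In that trial "both groups received supplemental rapid-acting insulin before meals for BG > 200 mg/dL", and earlier therapy other than metformin was stopped at entry.
- In the trial of basal insulin against oral agents, both with sliding scale, hypoglycemia occurred in 28% and 31% (p=0.37).
- In the retrospective cohort, admission treatment was "sliding scale regular insulin (25%), OADs (5%), insulin (34"%), with a further 26% on oral agents plus insulin.

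**The concern.** Regimen decides who enters the trial and is a plausible predictor of the primary safety outcome. With a small trial and no stated balancing, the arms can differ by chance in the share of residents not on scheduled insulin. Neither the chi-square test nor the center-only CMH test takes account of such a difference. The regressions might, but only if the analyst offers regimen as a candidate and the selection procedure keeps it.

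Two things are at stake. The first is precision, which this trial can ill spare: section 18 calls for 70 per group, while sections 1 and 12 give a total of 100. The second is the reading of this one trial. If a visible imbalance appears, a decision to adjust made after seeing the data will be open to challenge.

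**Working it through.** **Yardstick from the plan.** Section 18 plans for 60% against 35%, a difference of 25 points, with 70 per group. I assume alpha 0.05, because the plan states no level for this calculation. A two-sided test at 80% power gives

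n = [1.96 × √(2 × 0.475 × 0.525) + 0.8416 × √(0.60 × 0.40 + 0.35 × 0.65)]² / 0.25² = 61.4, so 62.

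The continuity correction raises this to 70. The plan's figure is therefore reproduced, though not by the one-sided test it names (49, or 56 with the correction). The plan gives no figure for imbalance by regimen, so the rest is my calculation.

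**Inputs**
- Share on sliding scale only: 25/(25 + 34 + 26) = 0.294, from the retrospective cohort. This is an assumption. It takes the other two groups as scheduled insulin and leaves out secretagogue-only residents, whose share is not given. If all of the 5% on oral agents qualified and were grouped with sliding scale, the share without scheduled insulin would be 30/90 = 0.333.
- 50 per arm: the total of 100, assuming simple 1:1 randomization.
- Rates, sliding scale only vs scheduled insulin: 3% vs 37% (linagliptin trial), 15% vs 37% (assumed midway case), and 31% vs 28% (oral agents plus sliding scale vs basal insulin).

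**Chance imbalance.** The SD of the between-arm difference in share is √(2 × 0.294 × 0.706 / 50) = 0.091. The 95% limit is 1.96 × 0.091 = 0.179. The exact binomial probability of an imbalance of at least 10 points is 0.323 (0.340 at a share of 0.333).

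**Effect on the comparison.** Shift in the risk difference = imbalance × rate gap. Share of variance explained = q(1−q) × gap² / [p(1−p)], where q is the share on sliding scale only and p is the pooled rate. At 3% vs 37%:
- p = 0.294 × 0.03 + 0.706 × 0.37 = 0.270
- total variance = 0.270 × 0.730 = 0.197
- between-regimen variance = 0.294 × 0.706 × 0.34² = 0.024
- share explained = 0.024/0.197 = 12.2%
- equivalent sample size ratio = 1/(1 − 0.122) = 1.14

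| Rates (sliding scale only vs scheduled) | Shift per 10-point imbalance | Shift at 95% limit | Variance explained | Equivalent sample size |
|---|---|---|---|---|
| 3% vs 37% | 3.4 points | 6.1 points | 12.2% | 1.14 |
| 15% vs 37% | 2.2 points | 3.9 points | 4.7% | 1.05 |
| 31% vs 28% | 0.3 points | 0.5 points | 0.1% | 1.00 |

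**Validity of the unadjusted test.** In simulation under no treatment effect (200,000 runs per scenario, 50 and 70 per arm, half the residents on each regimen, gaps of 3% vs 37%, 28% vs 37% and 28% vs 45%), the two-sided 5% test rejected in 4.9% to 5.2% of runs. The mean shift was zero to within 0.03 of a point.

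**The case against.** The strongest reply is that the documents do not show a risk gradient across the regimens this trial will actually enrol. A reader might infer from "fewer mild hypoglycemic events <70 mg/dL (3% vs. 37%, P <0.001") that criterion 2 pools risks running from 3% to 37%. It does not follow. The 3% belongs to a linagliptin arm in which other therapy except metformin had been withdrawn. A DPP4-inhibitor alone does not qualify a resident under criterion 2. That arm resembles only a resident on sliding scale with no secretagogue and no scheduled insulin, and no rate is reported for such residents as a group. The other randomized comparison, 28% vs 31%, shows essentially no gradient. This stands, and it makes 3% vs 37% an upper bound. It does not settle the matter the other way either: the 31% arm took oral agents as well, and the cohort's 45% figure combines oral agents (mostly sulfonylurea plus sliding scale) with insulin, so neither isolates sliding scale alone.

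A reader might also infer that the plan excludes regimen from adjustment. It does not. Safety models adjusted for confounders are planned, the named list is open, and that list belongs to the efficacy model. The accurate statement is that regimen is not prespecified. Likewise, the plan is silent on the randomization method; it does not rule out stratification.

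Finally, a reader might infer bias. Randomization makes the imbalance zero on average, and the unadjusted standard error already allows for it. That stands in full.

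**Conclusion.** The point holds as one of efficiency and prespecification. A factor that defines eligibility, probably predicts the outcome and is already recorded has no assured place in the randomization or in the safety analysis. The unadjusted test remains valid. The possible loss runs from almost nothing to about 12% of outcome variance, equivalent to about 14% more residents, with about 5% in the assumed midway case. Even at the upper bound, a 95%-limit imbalance moves the risk difference by 6.1 points against a planned 25.

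These figures rest on a 29% share on sliding scale only, on 50 per arm with simple randomization, and on rates from trials without CGM. Section 18 reports 56% by CGM against 14% by POC in one hospital study, so a gap between regimens seen with POC cannot be carried over to CGM. The size in this trial is therefore unknown. The change is worth making because it costs almost nothing.

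**What to change.** Define baseline regimen in the plan as a two-level factor, scheduled insulin yes or no, taken from the treatment recorded at baseline. Then:
- use it together with center to form the strata of the CMH test;
- force it into the logistic, count and time-in-range models as a fixed covariate, outside any stepwise selection;
- if randomization has not started, stratify randomization on it; if it has started, change the analysis only, before any comparison by arm.

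The cost is a sentence or two in section 18 and, if still possible, a revised randomization list. No new data are needed. The downside is some small strata: two levels across the three facilities named in section 23 make six, about 17 residents each on average. At a 29% share, the level without scheduled insulin would hold about 10 residents per facility (29/3) if the facilities recruit equally. That is the reason to prefer two levels to three. The two-level factor also groups secretagogue-only with sliding-scale-only residents, which may narrow the gap it captures. If the regimens prove to carry similar risk, the gain is small and little is lost.
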